Additional subscales, and some additional items on CCE that we will add will be used as secondary outcomes (see below). We will not use the weapon carrying, assault, intimate posting or hacking follow-on questions that were added to the ISRD4 as these are not required for calculating the primary outcome. The total number of delinquent acts will be used as the primary outcome measure.

Method of collection for offending and CCE data

There were significant problems with the SRDS measure (Smith & McVie, 2003) used in the pilot RCT. It was both highly positively skewed and the number of respondents admitting to criminal behaviour was very low. For 10 of the 15 questions, 80% or more of respondents said they had never engaged in these activities in the last six months (90%+ for six of the questions). There were only two questions to which at least half of YP admitted to engaging in at least once: truancy (52%) and fights (66%; although this includes fights with siblings). Furthermore, our limited examination of Protocol case files suggested that these responses were not honest.

We believe that this is due to characteristics of this population (minimisation, denial, fear of reprisal). It is likely that YP will fear reprisal from gangs or OCGs if it is discovered that they have told someone about their engagement in criminal activities. This is likely to be exacerbated by the need for us to include a disclaimer describing the conditions under which we would break confidentiality and disclose because if we are aware that YP are at risk of

being victimised then we have a duty of care to make a referral. The result is likely to be an unwillingness to provide honest responses to the questions in a self-report delinquency measure.

Our proposed solution is to keep primary outcome data and some secondary outcome data entirely anonymous until the end of the study. We will do this by explaining to YP that we will not look at the data until July 2026 and will facilitate this by adding a different ID number to these data than the main study ID used for other data. The study team will not have access to these data and they will be stored by another research team at the University of Greenwich, who will not have access to the main study ID. That study team will check for completeness of data but will not look at YP responses and will not be able to identify the YP from this data. Only at the end of the study will we link the two IDs.

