		Attachment representation measured by YP report: AAQ (Bodfield et al., 2020)	

YP self-efficacy measured by YP report: NGSE (Chen et al., 2001)

CU traits measured by YP and parent report: CU Traits MAP (Hawes et al., 2020)

Temperamental irritability measured by YP report: ODD subtyping DSM items (Stringaris & Goodman, 2009)

YP School attendance and truancy measured by parent report; and YP report from ISRD4

Age; gender; ethnicity; SES; household composition; parent relationship to YP measured by parent and/or YP report

Service being seen; days from first caseworker contact to randomisation measured by administrative data

Sample size calculations overview

Sample size calculations are not determined on the basis of a priori MDES but rather results from the pilot RCT.

		Protocol	Randomisation
Pilot study Effect Size		g = 0.36 [-0.32,1.03]	
Pre-test/ post- test correlations	level 1 (participant)	0.523	
Alpha ⁶		0.05	
Power		0.8	
One-sided or two-sided?		One sided	

⁶ Please adjust as necessary for trials with multiple primary outcomes, 3-arm trials, etc., when a Bonferroni correction is used to account for family-wise errors.

9

			Protocol	Randomisation
Number of participants		Intervention	144	
	of	Control	144	
	Total	288		

Sample size estimates for a full efficacy RCT were calculated using clincalc.com and checked against G^* Power calculations. Estimates used 80% power and p = 0.05 with an enrolment ratio of 1. Power calculations used one-sided tests because there is no recorded case of FFT having iatrogenic effects.

The primary outcome in the efficacy study is *Offending*: Self-reported delinquency (SRD) - International Self-Report Delinquency Study 4 survey offending scale (ISRD4; Marshall et al., 2022). This was not the primary outcome in the pilot study. Whilst a number of trials of FFT have been conducted with offending as a primary outcome, and a previous trial of FFT-G did include delinquency as a primary outcome, it recruited court mandated youth who were offending. The focus of the pilot was instead YP at risk of criminal exploitation recruited from social care.

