Therefore, the anticipated primary outcome in the pilot study was CCE as recorded on agency systems. During the pilot study, it became clear that this was not recorded reliably and so two co-primary outcomes collected directly from participants were used instead: PCG reported family functioning (total scale score) and YP reported conduct problems (CP; subscore of the SDQ). As a result, power calculations for this efficacy trial did not make use of SRD data from the pilot study. Based on the effect size for PCG-reported Family Functioning outcome in the pilot study (g = 0.36 (-0.32,1.03)), clincalc.com returned 238 participants, increased to 288 to account for up to 10% loss to follow-up at each assessment time point. Based on the effect size for YP-reported CP (g = 1.15 (0.13,1.52)), clincalc.com returned 42 participants, increased to 51 to account for 10% loss to follow-up at each assessment time point. After discussion with the YEF Assistant Director of Evaluation, the decision was taken to use the upper end of this sample size calculation range (N=288). Any harmful effects will be monitored through serious incident reporting. The pre-test/post-test correlation also mirrors the results of the pilot trial (i.e., 0.523).

However, as subsequently requested by the YEF, this trial will use self-reported delinquency as the primary outcome. The rationale for this is:

- A core YEF strategic aim is to understand what works to reduce crime and violence, so YEF aims to select offending as the primary outcome in all YEF studies where it is plausible that the intervention will reduce it, e.g. it is included in the theory of change
- The primary outcome must be measured using a valid and reliable measure and there were no valid and reliable measures of other relevant outcomes that are highly connected to crime e.g. child criminal exploitation.
- The mitigations included since the pilot study to increase the chance of seeing impact on offending (e.g. screening YP, introducing anonymous reporting of outcomes by YP)
- The co-primary outcomes from the pilot study will be included as secondary outcomes so that it will still be possible to test for intervention effects on these.

Participants

Participants will be YP between 10-17 at risk of CLDN involvement or CCE being seen by child social care or related agencies in three London local authorities and their primary caregiver (PCG).

Inclusion criteria - YP and families

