calculate effect sizes for primary and secondary outcomes. We will use structural equation modelling to test for mediators of treatment (which are listed as secondary outcomes above).

Based on evidence from the pilot trial it is possible that some outcome variables may be skewed, in particular the primary outcome. We will determine whether transformation or scaling is appropriate depending on the skew and distribution of the data.

The analytical approach has been determined a priori and will be conducted with R Studio and SPSS.

Primary outcome analysis

The primary outcome is the ISRD4 total score which is a continuous variable. All YP will complete this measure at baseline, 6 months after randomisation and 12 months after randomisation. The main test of treatment effect will be at 12 months after randomisation. The total score uses a sum of the total volume of delinquent acts using 14 questions. The response scale for each question can be from 0 to whatever the total number of acts reported is (although see above for transformation approach). A hierarchical linear mixed model will be used with site as a fixed effect.

Regression models will be adjusted by the baseline number of offences in the six months prior to randomisation and stratification factors; age group and site, as covariates. The regression model specification is detailed in eq. 1.

Eq. 1

OFF6i,j = α + β 1 (allocation)i,j + β 2 (OFF0)i,j + β 3 (age)i,j + β 4 (site)j + β 4 (study)j ϵ

Secondary outcome analysis

The secondary outcomes are:

- YP Child Criminal Exploitation measured by items added to the Self-Report Delinquency Scale (YP report).
- YP Substance Misuse measured by ISRD3 substance misuse subscale (YP report).
- YP Conduct Problems measured by the conduct problems subscale of the SDQ (YP and parent report).
- YP mental health and adjustment measured by total score and impact score on the SDQ (YP and parent report; impact score parent report only).
- Parental mental health measured by the DASS-21 (parent report).

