We will add three additional questions to the SRDS scale asking about missing from home episodes, storing or transporting drugs or weapons and engaging in sexual activity in exchange for money or goods. For each of these additional questions and for each of the 14 SRDS questions we will ask whether anyone has tried to involve the YP in these behaviours, who they were and how many times this happened. The CCE scale will be calculated from the total volume of how many times they were involved by others in these 17 behaviours and will range from 0 to the total number reported (although see above for transformation approach).

The ISRD3 substance misuse scale asks about the use of 5 substances, with response options varying depending on the substance. The scale can be from 0 to whatever the total number of times substances were used is (although see above for transformation approach). In addition, we will add questions on use of synthetic substances and on non-prescribed medications. We will calculate an additional total scale with these additional items and this will be analysed separately from the main ISRD3 substance misuse subscale.

SDQ subscales, including the conduct problems subscale, contain 5 items scored 0, 1 and 2, with scale values from 0 to 10. The SDQ total difficulties scale ranges does not include the prosocial scale and therefore ranges from 0 to 40. The impact score is computed by summing questions on distress and impairment and ranges from 0 to 10.

The DASS-21 contains 21 items, 8 for each of the anxiety, depression and stress subscales, with response values of 0, 1, 2 and 3. We will calculate the total score which ranges from 0 to 63.

All secondary outcome scores are treated as continuous, and a hierarchical linear mixed model will be used with site as a fixed effect. As noted above, we will determine whether transformation is appropriate depending on the data.

Subgroup analyses

Any subgroup analyses will be exploratory in nature. Sample size calculations for the trial have been conducted on the basis of the main primary outcome analysis, not for subgroup analyses. Therefore, it is possible that subgroup analyses may be underpowered. We will conduct post-hoc power analyses when all data has been collected and frame our reporting of these analyses accordingly. Analyses will be conducted using interaction terms.

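### The sample size was set on caregiver-reported family functioning, but the SAP twice attributes it to the primary outcome analysis and omits family functioning from its working list of secondary outcomes

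*SAP*

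**What the plan says.** The primary outcome is the ISRD4 total volume of delinquent acts, with the main test at 12 months (SAP, Primary outcome analysis).

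On the basis of N, SAP Sample size calculations overview is explicit: "Based on the effect size for PCG-reported Family Functioning outcome in the pilot study (g = 0.36 (-0.32,1.03)), clincalc.com returned 238 participants", raised to 288 for loss to follow-up. Of self-reported delinquency it says "As a result, power calculations for this efficacy trial did not make use of SRD data from the pilot study". The Protocol agrees in its Sample size calculations and Primary outcome sections. The stated design values are "Estimates used 80% power and p = 0.05 with an enrolment ratio of 1" and "Power calculations used one-sided tests because there is no recorded case of FFT having iatrogenic effects".

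Later, SAP Subgroup analyses says "Sample size calculations for the trial have been conducted on the basis of the main primary outcome analysis, not for subgroup analyses". Further analyses repeats the statement with mediation in place of subgroups.

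On family functioning, the sample size section gives as part of the rationale for changing the primary outcome that "The co-primary outcomes from the pilot study will be included as secondary outcomes". The SAP summary and design tables list SCORE-15 among the secondary outcomes. Secondary outcome analysis then opens its list with "The secondary outcomes are" and names criminal exploitation, substance misuse, SDQ conduct problems, SDQ total and impact scores, and DASS-21. SCORE-15 is not on it. In the analysis text it appears only under Further analyses, as an exploratory mediator.

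**The concern.** The two later sentences present the primary analysis as the one the trial was powered for, in contrast to subgroup and mediation analyses that may be underpowered. On the SAP's own account, that power belongs to another outcome, reported by another informant.

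The two measures also behave differently. SCORE-15 runs from 15 to 75. The ISRD4 total has no upper bound, and the SAP expects it may be skewed. Of the pilot's delinquency measure, a different instrument, the Protocol says "It was both highly positively skewed and the number of respondents admitting to criminal behaviour was very low". A standardised effect from the family functioning scale has no stated meaning for the offending count.

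Two things are at stake. If the later sentences carry through to the report, a null primary result could be presented as coming from a trial with 80% power for that outcome. And the outcome that fixed N has no treatment-effect analysis set out in the section that specifies such analyses, although its retention was part of the case for changing the primary outcome.

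**Working it through.** **1. Reproducing the plan's N.** Inputs from SAP Sample size calculations overview: g = 0.36, alpha 0.05, power 80%, allocation 1:1. Formula: n per arm = 2(z_a + z_b)^2 / g^2.

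- Two-sided: 2 x (1.960 + 0.842)^2 / 0.36^2 = 121.1, so 122 per arm and 244 in total, within 3% of 238.
- One-sided, as stated: 2 x (1.645 + 0.842)^2 / 0.36^2 = 95.4, so 96 per arm and 192 in total, which does not match.
- Attrition: 238 x 1.1 x 1.1 = 287.98, so 288.

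So 288 traces to the family functioning effect. With 238 analysed, g = 0.36 has 79% power two-sided and 87% one-sided; the 80% fits a two-sided calculation although both documents state one-sided. The correlation 0.523 is described only as mirroring the pilot, with no outcome named, and is not needed to get near 238.

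**2. Passages side by side.**

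| Question | Sample size section and tables | Later analysis text |
|---|---|---|
| What was N based on? | Caregiver-reported family functioning; no delinquency data | Main primary outcome analysis (stated twice) |
| Is SCORE-15 a secondary outcome? | Yes (rationale; summary and design tables) | Not in the secondary list; exploratory mediator only |

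**3. Detectable effect on a standardised scale.** Completers: 288 x 0.9 x 0.9 = 233. Formula: (z_a + z_b) x sqrt(4/233).

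- Unadjusted: 2.486 x 0.131 = 0.33 one-sided; 2.802 x 0.131 = 0.37 two-sided.
- If r = 0.523 is assumed to carry over to the count, multiply by sqrt(1 - 0.523^2) = 0.852: 0.28 one-sided, 0.31 two-sided.

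**4. Illustration for a count.** The documents give no ISRD4 mean, SD or dispersion. Assume a negative binomial count with control mean m from 2 to 10 and dispersion k from 1 to 5 (9% to 62% zeros), 116.5 per arm, no baseline adjustment. Solve

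ln RR = -(z_a + z_b) x sqrt[(1/m + 1/(m RR) + 2k) / 116.5].

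- m = 10, k = 1, one-sided: sqrt(2.241/116.5) = 0.139; 2.486 x 0.139 = 0.345; RR = 0.71. Two-sided: 0.68.
- m = 2, k = 5, one-sided: sqrt(11.60/116.5) = 0.316; 2.486 x 0.316 = 0.784; RR = 0.46. Two-sided: 0.41.

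**5. What g = 0.36 would mean for such a count.** SAP Presentation of outcomes defines g with the pooled SD of both arms, so solve

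m(1 - RR) / sqrt{[m + k m^2 + m RR + k(m RR)^2] / 2} = 0.36.

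- m = 10, k = 1: difference 3.24, pooled SD sqrt[(110 + 52.4)/2] = 9.01; a 32% reduction.
- m = 2, k = 5: difference 1.28, pooled SD sqrt[(22 + 3.31)/2] = 3.56; a 64% reduction.

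**The case against.** The SAP discloses the true basis. Its sample size section names family functioning as the source of 238 and 288, says delinquency data were not used, and explains why the primary outcome changed. The two later sentences are asides in sections on other analyses. This stands: it is an internal contradiction, not concealment. But those asides are where the SAP says how underpowered analyses will be framed in reporting, so the error should not stay.

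SCORE-15 is still called secondary in both SAP tables. The Analysis section says the mediators are among the secondary outcomes and applies the intention-to-treat mixed model to primary and secondary outcomes generally. A reader might infer from the shorter list that family functioning has been dropped; the documents do not support that. However, the tables also place age, gender and ethnicity under secondary outcomes, so they cannot by themselves define what is tested. The lists need reconciling.

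A reader might also infer that the trial is underpowered for offending. That is not shown either. The pilot's skew comes from another instrument, without the new anonymous collection; the SAP plans baseline adjustment and possible transformation of a linear model. The rate ratios in the working belong to a different, unadjusted model and rest on assumed means and dispersions, so they only illustrate scale. Dividing by the control-arm SD alone would turn g = 0.36 into a 38% to 84% cut, but the SAP's g uses the pooled SD.

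**Conclusion.** The SAP contradicts itself on what its sample size was based on. N = 288 follows from the pilot effect on caregiver-reported family functioning, and nothing in either document links 80% power to the ISRD4 count. Power for the primary outcome is unsupported; the documents show neither that it is adequate nor that it is inadequate. Separately, the promise to keep both pilot co-primaries as secondary outcomes is carried into the working list for conduct problems only.

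The contradiction and the omission rest on the documents' own text and need no assumption. The detectable 0.33 SD (one-sided, unadjusted) needs only the planned attrition. The rate ratios of 0.71 to 0.46 (0.68 to 0.41 two-sided) and the 32% to 64% reduction corresponding to g = 0.36 hold only under the stated negative binomial assumptions.

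**What to change.** 1. Correct the sentences in Subgroup analyses and Further analyses: the sample size was based on caregiver-reported family functioning, and no power is claimed for ISRD4.
2. Add a short table of the detectable ISRD4 effect, matched to the stated sidedness and the planned model, with every assumption labelled. The figures in the working can serve as an illustration; they should not be entered as established values.
3. If pooled, arm-blind ISRD4 data are used to update that table, do so only after July 2026, the date until which young people are told their answers will not be looked at, and before the two sets of IDs are linked. The November 2025 SAP update in the Protocol's Timeline falls too early for this step; the wording changes need not wait.
4. Add the caregiver-reported SCORE-15 total at 12 months to the list in Secondary outcome analysis, with the same intention-to-treat mixed model, and reconcile that list with the SAP's two tables. Its mediator role can remain.

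Cost: SAP wording, one short table, and a less favourable power statement. SCORE-15 is already collected, and neither N nor data collection changes.

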These analyses were planned after the protocol, but before the commencement of the trial. We will explore potential mediators of treatment using Structural Equation Modelling. These analyses will be exploratory in nature. Sample size calculations for the trial have been conducted on the basis of the main primary outcome analysis, not for mediation analyses. Therefore, it is possible that mediation analyses may be underpowered. We will conduct post-

hoc power analyses when all data has been collected and frame our reporting of these analyses accordingly.

We will test the following mediators:

- Parental supervision, knowledge and child disclosure, measured by ISRD3 subscales, 12 items, scale ranges from 0 to 48.
- Family functioning measured by SCORE-15, 15 items, scale ranges from 15 to 75.
- Attachment representation using the AAQ, 9 items, scale ranges from 0 to 36.
- Parental self-efficacy measured by the BPSES, 5 items, 5 to 15.
- YP self-efficacy using the NGSE, 8 items, scale ranges from 8 to 40.

We would anticipate conducting analyses comparing the explanatory power of individual YP vs. parent/family factors in predicting mediation of treatment effect, covarying for baseline values of outcomes.

Interim analyses and stopping rules

We do not plan to conduct interim analyses. We will monitor data completion and missing data rates and monitor and report adverse events. The trial will stop if the YEF, FPM and the University of Greenwich decide that the trial is unable to recruit a sufficient number of participants.

Longitudinal follow-up analyses

No longitudinal analyses other than those to test treatment effects will be conducted.

Imbalance at baseline

We will produce a table of baseline characteristics by trial arm, including age, ethnicity, gender, school attendance, CU traits, temperamental irritability, offending at baseline and outcomes. We will report means and standard deviations and counts and percentages with histograms of baseline data. We will not formally test for imbalance at baseline but will address any effects of potential imbalance using the missing data strategy specified below.

Missing data

We will report on rates of missing data of all measures by treatment group. We will use logistic regression models to identify predictors of missingness and include these as covariates in analyses of outcomes described above. If levels of missing data warrant it, we will consider

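### Subgroup and mediation results are to be framed by post-hoc power whose effect size the SAP does not fix; confidence intervals would answer the question better

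*SAP*

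**What the plan says.** SAP, Subgroup analyses, gives these analyses a modest status: "Any subgroup analyses will be exploratory in nature". It explains that "Sample size calculations for the trial have been conducted on the basis of the main primary outcome analysis, not for subgroup analyses", warns that "Therefore, it is possible that subgroup analyses may be underpowered", and then commits: "We will conduct post-hoc power analyses when all data has been collected and frame our reporting of these analyses accordingly". On method it adds "Analyses will be conducted using interaction terms".

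SAP, Further analyses, treats mediation in the same way. The analyses are called exploratory, the warning is "Therefore, it is possible that mediation analyses may be underpowered", and the section promises post-"hoc power analyses when all data has been collected and frame our reporting of these analyses accordingly".

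Neither section names the effect size, a power threshold, or how the wording of a result would depend on the power obtained. Elsewhere, SAP, Analysis, plans effect sizes for the primary and secondary outcomes, and SAP, Presentation of outcomes, gives a confidence interval for a two-group Hedges' g. No interval is specified for an interaction or an indirect effect.

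**The concern.** Power is a planning quantity. Once the data are in, what a reader needs from a moderator or mediation analysis is the estimate and the range of effects compatible with it. The SAP instead lets a power figure decide how the result is presented, and leaves open the input that determines the figure.

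There are two possibilities. Power at the observed effect repeats the p-value in another form. Power at a target effect is a legitimate calculation, but the SAP fixes no target interaction or indirect effect, so the target would be picked when results could already be in view. Nor is there a ready design value to fall back on: by SAP, Sample size calculations overview, g = 0.36 comes from caregiver-reported family functioning in the pilot, and the power calculations did not use pilot delinquency data.

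The stake is the answer to research questions 3 and 4 (Protocol, Research questions or study objectives). SAP, Subgroup analyses, asks whether the therapy works as well for minoritised young people as for White young people, and as well for females as for males. A non-significant interaction answers that only through an interval showing how large a difference has been ruled out.

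**Working it through.** The documents give no power or detectable-effect figure for subgroups or mediation, so there is no stated figure to reproduce.

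**Step 1. Power at the observed effect.** For a two-sided z test at 0.05 of a single coefficient, let z_obs = Φ⁻¹(1 − p/2). Then

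observed power = Φ(z_obs − 1.96) + Φ(−z_obs − 1.96).

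The only input is p.

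| p | observed power |
|---|---|
| 0.001 | 91% |
| 0.01 | 73% |
| 0.05 | 50% |
| 0.10 | 38% |
| 0.20 | 25% |
| 0.50 | 10% |
| 0.80 | 6% |

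Observed power reaches 80% only when z_obs is about 1.96 + 0.84 = 2.80, that is, p of about 0.005. The identity is exact for one interaction coefficient. It is approximate for an indirect effect, which is a product of coefficients.

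**Step 2. Power at a fixed target.** With a prespecified effect and the achieved N, split and SD, power does not depend on p and the circularity does not arise. This route needs a target, and the SAP has none.

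**Step 3. What can be said before the data.** Inputs from SAP, Sample size calculations overview: N = 288; up to 10% loss at each of two follow-ups; 1:1 allocation; 80% power; alpha 0.05; pilot pre/post correlation 0.523. Completers: 288 × 0.9 × 0.9 = 233. My assumptions: a binary moderator with share s, SD = 1, s = 0.5 or 0.2 (the documents give no shares), a two-sided test, and the pilot correlation carried over to the delinquency outcome where adjustment is shown.

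SE of the interaction = √[4/(N·s) + 4/(N·(1 − s))]

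- s = 0.5: √(4/116.5 + 4/116.5) = 0.262
- s = 0.2: √(4/46.6 + 4/186.4) = 0.328

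Smallest detectable interaction = (1.960 + 0.842) × SE. Baseline adjustment multiplies this by √(1 − 0.523²) = 0.852.

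| split | unadjusted | baseline-adjusted |
|---|---|---|
| 50/50 | 0.73 SD | 0.63 SD |
| 80/20 | 0.92 SD | 0.78 SD |

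The main design is one-sided, and sidedness for interactions is not stated. One-sided at 50/50, unadjusted, the figure is (1.645 + 0.842) × 0.262 = 0.65 SD.

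For comparison, power for an interaction as large as the design effect of 0.36 SD, at 50/50 and two-sided, is Φ(0.36/0.262 − 1.96) = 28% unadjusted and Φ(0.36/0.223 − 1.96) = 36% adjusted (the opposite tail is negligible). The unadjusted detectable interaction at 50/50 is about twice the design effect: 0.73/0.36 = 2.0.

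**The case against.** The strongest reply is that the SAP never says the observed effect will be used. It says only when the power will be computed. Power at a sensible target with the achieved sample and variance would also be computed then, and would be informative. The sentence also follows a warning that the analyses may be underpowered, so it can be read as a caution against over-interpretation. This stands as far as it goes: the charge of circularity is conditional. It does not rescue the plan, because the target is missing.

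A reader might infer that the SAP will label every null result underpowered. The documents do not support that: there is no threshold and no rule for null results. A reader might equally infer that every significant interaction would look adequately powered. Step 1 contradicts this: against the SAP's only power standard ("80% power and p = 0.05 with an enrolment ratio of 1"), a result with p between about 0.005 and 0.05 would fall short at the observed effect.

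The detectable-effect figures can also be challenged, and fairly. Age is analysed as continuous, and callous-unemotional traits and irritability are scored on scales, so the binary formula fits only gender and caseworker-reported offending directly. The Black/White and South Asian/White contrasts are likely to use fewer than all completers. The SAP expects that the primary outcome may be skewed and transformed. The figures show the order of size only.

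**Conclusion.** The point holds in a limited form. In both sections the SAP makes post-hoc power the basis for framing results without fixing its effect size. On one reading the power is uninformative; on the other its decisive input is left until after the data are collected. On either reading it does not show which effects the data exclude, and the SAP plans no interval for interactions or indirect effects that would.

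The first part rests on the usual meaning of post-hoc power and is exact only for single-coefficient tests. The indicative detectable interactions, 0.63 to 0.92 SD across the two assumed splits with and without adjustment (two-sided), rest on the assumptions in Step 3. No figure is offered for mediation. The impact is small: both sets of analyses are declared exploratory, and no primary or secondary conclusion depends on them.

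**What to change.** Delete the post-hoc power sentence from SAP, Subgroup analyses, and from SAP, Further analyses. In its place:

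- Report every interaction and every indirect effect with a 95% confidence interval, using a bootstrap interval for indirect effects, and word conclusions by what the interval excludes.
- State now the smallest interaction detectable at the planned N, with the assumed subgroup share, number of completers, sidedness and baseline correlation shown. Express it in a form suited to each moderator: a difference between groups for binary ones, a slope for age and the trait scales.

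The cost is a change of SAP wording. It needs no new data and less work than the planned power runs.
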